AM 3.1	
At the Week 36, Week 52, and Week 104 visits, DXA is required.
 
 • For Early Termination occurring before Week 36, DXA is not required at the Early Termination visit unless it will aid in the assessment of an adverse event or if the most recent DXA bone mineral density loss at lumbar spine (L1-L4) or total hip was > 2% relative to the pivotal phase 3 study baseline. • For Early Termination occurring at or after the Week 36 visit, DXA is required at Early Termination unless a DXA result is available from within six weeks prior to Early Termination. 	
Post-Treatment DXA is required at 6 months (± 1 month):
 
 • For Early Termination occurring before Week 36: 
 – the most recent DXA bone mineral density loss at lumbar spine (L1-L4) or total hip was > 2% relative to the pivotal phase 3 study baseline. • For Early Termination occurring at or after the Week 36 visit: 
 – the most recent DXA scan was at Week 24 and on the most recent DXA scan, bone mineral density loss at the lumbar spine (L1-L4) or total hip was > 2%, relative to the pivotal phase 3 study baseline. – the most recent DXA was after the Week 24 visit and on the most recent DXA scan, bone mineral density loss at the lumbar spine (L1-L4) or total hip was > 3%, relative to the pivotal phase 3 study baseline. • For patients who complete the open-label extension study: 
 – at the Week 104 visit or on the most recent DXA scan, bone mineral density loss at the lumbar spine (L1-L4) or total hip was > 3%, relative to the pivotal phase 3 study baseline. 
12-Month Post-Treatment DXA: patients have 6-month post-treatment follow-up scans that show bone loss of > 1.5% at the lumbar spine and/or > 2.5% at total hip compared with the pivotal phase 3 study baseline, patients are strongly encouraged to come back to the clinic for an additional post-treatment follow

[figure not shown]

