
AM 4.0
	
 • For Early Termination occurring before Week 36, DXA is not required at the Early Termination visit unless it will aid in the assessment of an adverse event or if the most recent DXA BMD loss at lumbar spine (L1-L4) or total hip was > 2% relative to the parent study baseline. • For Early Termination occurring at or after Week 36, DXA is required at Early Termination unless a DXA result is available from within six weeks prior to Early Termination. 	
6-month and 12-Month Post-Treatment DXA:
 
 • All ongoing patients, after they complete the Week 104 visit or terminate the study early, will return for a 6-month PTFU DXA and a 12-month PTFU DXA • All patients who completed treatment or terminated from the study early and are within 6 months from their last day on treatment will be requested to return for a 6month PTFU DXA and again for a 12-month PTFU DXA. • All patients who completed treatment or terminated from the study early and are past 6 months but within 12 months from their last day on treatment will be requested to return for a 12-month post-treatment DXA. • For patients who are outside the PTFU visit windows, PTFU DXA is still recommended. However, if the patient is beyond 14 months from last day on treatment, she does not need to return for 12-month post-treatment DXA. 
If patients have 6-month or 12-month PTFU scans that show bone loss of $\geq 3\%$ at the lumbar spine and/or total hip compared with the parent study baseline, patients should be referred to and strongly encouraged to see a bone specialist for further evaluation of the bone loss.

---------------	--	---

The 6-month and 12-month PTFU visits will also measure post-treatment medical and gynecological history, concomitant medications, and bone fracture events. Patients should also have the following clinical laboratory evaluations: vitamin D, thyroid-stimulating hormone, parathyroid hormone, creatinine, calcium, and phosphorous at the 6-month and 12-month PTFU visit only if PTFU scans show a bone loss of $\geq 3\%$ at the lumbar spine and/or total hip compared with the parent study baseline.

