Week 12	64	85	106
Week 24	148	169	196
Week 36	197	253	308
Week 52	309	365	421
Week 104	647	731	815
6-month post-treatment Follow-Up	Date of last dose + 150 days	Date of last dose + 180 days	Date of last dose + 304 days
12-month post-treatment Follow-Up	Date of last dose + 305 days	Date of last dose + 365 days	Date of last dose + 425 days

Table 5: Visit Windows for ECG Assessments

Visit	Start Day	Target Day	End Day
Week 12	64	85	106
Week 24	148	169	196
Week 52	309	365	421
Week 104	675	731	787

Table 6: Visit Windows for EHP-30 Questionnaire Assessments

Visit	Start Day	Target Day	End Day
Week 12	64	85	106
Week 24	148	169	196
Week 36	197	253	308
Week 48	309	337	351
Week 52	352	365	421
Week 78	491	547	603
Week 104	675	731	787

Table 7: Visit Windows for EHP Work Domain and EQ-5D-5L Assessments

Visit	Start Day	Target Day	End Day
Week 24	128	169	196
Week 52	309	365	421
Week 78	491	547	603
Week 104	675	731	787

Table 8: Visit Windows for PGIC Assessments

Visit	Start Day	Target Day	End Day
Week 12	64	85	106
Week 24	148	169	196
Week 36	197	253	308
Week 52	309	365	421

Table 9: Visit Windows for Endometrial Biopsies Assessments

Visit	Start Day	Target Day	End Day
Week 24	128	169	196
Week 52	309	365	421
Week 104	675	731	787
Safety Follow-Up ^a	Date of last dose + 7 days	Date of last dose + 30 days	Date of last dose + 60 days

^a Assessments will be excluded from analysis if they occur on or after the date of initiation of another investigational agent or hormonal therapy affecting the hypothalamic- pituitary- gonadal axis or surgical intervention for endometriosis-associated pain. Assessments after date of last dose of extension study drug + 30 days will also be excluded from analysis.

Table 10: Visit Windows for Mammogram Assessments

Visit	Start Day	Target Day	End Day
Week 52	309	365	421
Week 104	675	731	787

For patients who are or become ≥ 40 years old during the study.

Mammogram assessments are required only by protocol amendment 3.0 and 3.1.

Table 11: Time Windows for Daily Assessments from eDiary

Visit	Target Study Day of Visit ^a	Days Included in Assessment Period Window
Week 4	X ₁	1 to X ₁
Week 8	X ₂	(X ₂ - 34) to ≤ X ₂
Week 12	X ₃	(X ₃ - 34) to ≤ X ₃
Week 16	X ₄	(X ₄ - 34) to ≤ X ₄
Week 20	X ₅	(X ₅ - 34) to ≤ X ₅
Week 24	X ₆ ^b	(X ₆ - 34) to ≤ X ₆
Week 28	X ₇	Maximum [OLE start day ^c , (X ₇ - 34)] to ≤ X ₇
Week 32	X ₈	Maximum [OLE start day ^c , (X ₈ - 34)] to ≤ X ₈
Week 36	X ₉	(X ₉ - 34) to ≤ X ₉
Week 40	X ₁₀	(X ₁₀ - 34) to ≤ X ₁₀

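### The 6-month post-treatment BMD window runs from 30 days before to 124 days after its target, so a scan nearly 10 months off drug can be reported as the 6-month value

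*SAP*

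**What the plan says.** Table 4 in SAP Section 4.3.8 defines two post-treatment BMD windows, counted from the last dose:

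- 6-month: start "Date of last dose + 150 days", target "Date of last dose + 180 days", end "Date of last dose + 304 days".
- 12-month: start "Date of last dose + 305 days", target "Date of last dose + 365 days", end "Date of last dose + 425 days".

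The same section keeps one result per window, the non-missing one closest to the target, and says the windows serve only the by-visit summaries.

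Table 2 in Section 2.1 gives the scan timing by protocol version. The entries for Amendments 2.0 and 3.1 read "Post-Treatment DXA is required at 6 months (± 1 month"; the original protocol and Amendment 1.0 use the same tolerance. The Amendment 4.0 entry states no such tolerance. It says that women who are "past 6 months but within 12 months from their last day on treatment will be requested to return for a 12-month post-treatment DXA", still recommends a scan for women outside the follow-up visit windows, and drops the 12-month scan beyond 14 months.

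Percent BMD change at 6 and 12 months post-treatment is a safety endpoint in Section 1.1, Table 1. Section 9.3.5 summarizes recovery of BMD loss from the same two visits.

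**The concern.** The two post-treatment visits exist to show what happens to BMD at different times after stopping treatment, so time since last dose is the quantity of interest. The 6-month window spans about 5 months of it. A value labelled 6-month may come from a woman who has been off drug for 5 months or for 10. The late end of the window also takes scans that lie nearer the 12-month target.

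Late or off-schedule scans are foreseeable. Amendment 4.0 calls back women who had already passed 6 months and recommends scans even outside the visit windows. A scan requested as a 12-month scan can then be filed under 6 months. The BMD results are descriptive and the visit label carries their interpretation. A table reader has no means of seeing how much the label departs from actual time off drug.

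**Working it through.** **Inputs.** All window bounds and targets are from Table 4. The month length, 30.4375 days, is from Section 4.1. The closest-to-target rule is from Section 4.3.8.

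**Width around each target.**
- 6-month: 180 - 150 = 30 days before; 304 - 180 = 124 days after.
- 12-month: 365 - 305 = 60 days before; 425 - 365 = 60 days after.

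**Where the bound of 304 comes from.** It is the day before the 12-month window opens (365 - 60 - 1 = 304). It does not follow from 6 months plus 1 month, which would be 180 + 30 = 210 days, or 7 × 30.4375 = 213 days.

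**Time off drug at the bound.** 304 / 30.4375 = 9.99 months, and 304 / 180 = 1.69 times the target interval.

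**Share of the window far from target.** The window holds 304 - 150 + 1 = 155 days. Days 211 to 304 lie more than 30 days past target: 94 days, and 94 / 155 = 61%. This is a share of calendar days, not of patients.

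**Nearest target.** The midpoint is (180 + 365) / 2 = 272.5. Days 273 to 304, which is 32 days, are closer to 365 but are labelled 6-month. Day 304 is 124 days from the 6-month target and 365 - 304 = 61 days from the 12-month target.

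**The closest-to-target rule applied to example scan days under the current Table 4.**

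| Scans (days after last dose) | 6-month value | 12-month value |
|---|---|---|
| 300 only | 300 | none |
| 180 and 290 | 180 | none (290 unused) |
| 200 and 300 | 200 | none (300 unused) |
| 285 and 365 | 285 | 365 |

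**The same rule with the cut moved to 272/273.**

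| Scans | 6-month value | 12-month value |
|---|---|---|
| 300 only | none | 300 |
| 180 and 290 | 180 | 290 |
| 200 and 300 | 200 | 300 |
| 285 and 365 | none | 365 (285 unused) |

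Under the moved cut the 6-month window is -30/+92 days (272 - 180 = 92) and the 12-month window -92/+60 (365 - 273 = 92).

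**The case against.** The present cut has a visible logic. The 12-month window is symmetric, and its end, 425 / 30.4375 = 13.96 months, agrees with the 14-month limit in Amendment 4.0. The 6-month window is extended to meet it so that no scan falls in a gap. This protects the 12-month estimate from early scans. A midpoint rule is not universal in Table 4 either: Week 24 ends at day 196, although the midpoint of targets 169 and 253 is 211. All analyses are descriptive. The midpoint cut has its own cost, since the pair at 285 and 365 loses its earlier scan. All of this stands, and it makes the choice of cut a matter of judgement.

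It does not justify calling a scan at almost 10 months a 6-month scan. The nearest-target cut leaves no gap and covers the same days. Midpoint splits are also used elsewhere, for example Week 36/52 in Table 4 (split 308/309, midpoint 309).

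Four stronger readings are tempting but unsupported:

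- **Early 12-month scans are generally lost.** Only scans before + 305, more than 60 days early, leave the 12-month summary. They drop out of both by-visit summaries only if a scan closer to + 180 exists.
- **Late scans replace timely ones.** The closest-to-target rule prevents that.
- **The window breaches the plus or minus 1 month rule.** That tolerance belongs to the table entries before Amendment 4.0, on which the SAP is based. It governs scheduling, and an analysis window may be wider.
- **Early recovery is overstated by a known amount.** A straight line to complete recovery at day 365 would give 304/365 = 83% at the bound against 180/365 = 49% at target. The SAP gives no trajectory, and one edge scan says nothing about a group mean.

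**Conclusion.** The point holds as a weakness in how the 6-month window is set. The window is -30/+124 days, admits scans up to 9.99 months off drug where no scan closer to + 180 exists, and gives 32 days to the farther target. The direction of any distortion, 6-month results drawn toward 12-month results, rests on the assumption that BMD recovers with time off drug. Its size cannot be computed, because the SAP gives neither scan dates nor the number of women with only a late scan. It could be negligible if few scans fall between + 211 and + 304. The case for change rests on the small cost of labelling scans transparently, not on a demonstrated bias.

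**What to change.** In Table 4, end the 6-month window at last dose + 272 days and start the 12-month window at + 273, leaving + 150 and + 425 unchanged. In Section 9.3.5, add two items:

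1. a 6-month sensitivity summary limited to about + 150 to + 210 days;
2. the median and range of days since last dose at each post-treatment visit.

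This concerns the analysis windows only and changes no scan schedule. The cost is two numbers in Table 4, one extra summary and one descriptive line, with no new data.

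The downside should be stated in the SAP. The 12-month window becomes -92/+60, so a scan at 273 / 30.4375 = 8.97 months counts as 12-month. A woman with two scans in it, such as + 285 and + 365, loses the earlier one from the by-visit summary. If the sponsor prefers the current cut for that reason, a sentence giving the rationale would suffice for Table 4, but both additions to Section 9.3.5 should still be made.

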4.4. General Rules for Missing Data

The rules for handling missing data for by-visit endpoints and incomplete dates associated with adverse events and concomitant medications are discussed in this section. Handling of missing data for the primary efficacy analyses are described in Section 7.2.4.

4.4.1. By-Visit Endpoints

By-visit endpoints will be analyzed using observed data, unless otherwise specified. For observed data analyses, missing data will not be imputed and only the observed records will be included.

4.4.2. Adverse Events and Concomitant Medications

The following imputation rules for the safety analyses will be used to address the issues with partial dates. The imputed dates will be used to determine the treatment-emergent period. For adverse events with a partial date, available date parts (year, month, and day) of the partial date will be compared with the corresponding date components of the start date and end dates of the treatment-emergent period to determine if the event is treatment emergent. When in doubt, the adverse event will be considered treatment emergent by default.

The following rules will be applied to impute partial dates for adverse events:

- If start date of an adverse event is partially missing, impute as follows:
 - If both Month and Day are missing and Year = Year of extension study treatment start date, then set to extension study treatment start date, as long as adverse event end date is not prior to extension study treatment start date;
 - If both Month and Day are missing and Year \neq Year of extension study treatment start date, then set to January 1;
 - If Day is missing and Month and Year = Month and Year of extension study treatment start date, then set to extension study treatment start date, as long as adverse event end date is not prior to extension study treatment start date;
 - If Day is missing and Month and Year \neq Month and Year of extension study treatment start date, then set to first of the month;
 - If start date is completely missing, set to extension study treatment start date, as long as adverse event end date is not prior to pivotal phase 3 study treatment start date.
- If end date of an adverse event is partially missing, impute as follows:
 - If both Month and Day are missing, then set to December 31;
 - If only Day is missing, then set to last day of the month;
 - If end date is completely missing, do not impute.

When the start date or end date of a medication is partially missing, the date will be imputed to determine whether the medication is prior or concomitant (or both).

The following rules will be applied to impute partial dates for medications:

- If start date of a medication is partially missing, impute as follows:
 - If both Month and Day are missing, then set to January 1;
 - If only Day is missing, then set to the first of the month.
- If end date of a medication is partially missing, impute as follows:
 - If both Month and Day are missing, then set to December 31;
 - If only Day is missing, then set to last day of the month.

If start date or end date of a medication is completely missing, do not impute.

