4.3.3. Study Day

Study day will be calculated with respect to the date of the first dose of study drug in the pivotal phase 3 study (Study Day 1). For assessments conducted on or after the date of the first dose of pivotal phase 3 study drug, study day will be calculated as:

$$(\text{Assessment date} - \text{date of first dose of pivotal phase 3 study drug}) + 1$$

For assessments conducted before the date (and time) of the first dose of pivotal phase 3 study drug, study day will be calculated as:

$$(\text{Assessment date} - \text{date of first dose of pivotal phase 3 study drug})$$

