9.1. Adverse Events

Adverse events will be collected from the time of the first dose of open-label study drug through the safety Follow up visit approximately 30 days after the last dose of open-label study drug (the end of extension treatment period), or the date of initiation of another investigational agent or hormonal therapy or surgical intervention affecting the hypothalamic-pituitary-gonadal axis or surgical intervention for endometriosis, whichever occurs first, as also specified in the Schedule of Activities in the study protocol Section 1.1. Additionally, serious adverse events reported to the investigator after the safety reporting period should be reported to the sponsor regardless of causal relationship to study drug treatment.

Using a Safety Report Form, all serious adverse events must be reported within 24 hours of the study site personnel's knowledge of the event, regardless of the investigator assessment of the relationship of the event to study drug.

The severity of all treatment-emergent adverse events will be evaluated by the investigator based on the National Cancer Institute's Common Terminology Criteria for Adverse Events (CTCAE, version 5.0 dated 27 Nov 2017), and will be coded to preferred term and system organ class using MedDRA 22.0 or higher.

A treatment-emergent adverse event is defined as any adverse event that occurs after administration of the first dose of pivotal phase 3 study drug.

Adverse event summaries will be based on treatment-emergent adverse events in the pivotal phase 3 and extension studies, unless otherwise specified. All adverse events in the pivotal phase 3 and extension studies will be listed in by-patient listings.

The following tabular summaries that include the number and percentage of patients will be provided:

- Overview of adverse events;
 - Safety parameters of interest

- Safety parameters of interest with first onset during extension study
- All adverse events;
 - By SOC and PT;
 - By decreasing frequency of PT;
 - By SOC, PT, and maximum severity;
 - Study drug-related per investigator by SOC and PT;
 - By time to onset (Day 1 to Week 24, > Week 24 to Week 52, >Week 52 to Week 78, > Week 78 to Week 104, > Week 104), SOC and PT;
 - Exposure-adjusted AE rate by SOC and PT
- Adverse events reported in at least 5% of patients in any treatment group
 - By decreasing frequency of PT;
- Grade 3 or above adverse events;
 - By SOC and PT;
 - By decreasing frequency of PT;

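### SAP Section 4.4.2 anchors partial adverse event start dates on the extension start alone, so pivotal-study events can be dated to the extension or to before Study Day 1

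*SAP*

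**What the plan says.** Section 4.4.2 of the SAP gives date-imputation rules for the safety analyses and does not limit them to events recorded in the extension. For partial start dates there are four rules:

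- Month and day missing, year equal to that of the extension start: "Year = Year of extension study treatment start date, then set to extension study treatment start date", unless the event ended before the extension start.
- Month and day missing, year different from "Year of extension study treatment start date, then set to January 1".
- Day missing, month and year equal to those of the extension start: the extension start date, with the same end-date condition.
- Day missing, month and year different from "Month and Year of extension study treatment start date, then set to first of the month".

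The section also compares the known date parts with the treatment-emergent period and treats doubtful events as treatment-emergent.

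Elsewhere the reference point is the pivotal study. Section 9.1: "A treatment-emergent adverse event is defined as any adverse event that occurs after administration of the first dose of pivotal phase 3 study drug". Section 4.3.3 numbers days from the same origin: "Study day will be calculated with respect to the date of the first dose of study drug in the pivotal phase 3 study (Study Day", with that date as the first day. Section 9.1 on scope: "Adverse event summaries will be based on treatment-emergent adverse events in the pivotal phase 3 and extension studies, unless otherwise specified". Section 9.1 then asks for a table "By time to onset (Day 1 to Week 24, > Week 24 to Week 52" and onward in further bands, and for a series of tables of events with first onset during the extension.

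**The concern.** The imputation anchor and the analysis origin are 24 weeks apart. A rule built around the extension start suits events that arise in the extension. The pooled summaries also contain events that arose in the pivotal study, and for those the rules can move onset in either direction.

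At stake are the displays that separate early from later risk: the time-to-onset table, and the first-onset-during-extension tables (all events, serious, Grade 3 or above, leading to withdrawal, mood, vasomotor, bone, hepatic, metabolic). In the former placebo group, an event that began on placebo could be shown as beginning after the switch to active treatment.

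**Working it through.** The plan gives no figure on this point, so there is none to reproduce. The check applies the four written rules to pivotal-onset events.

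**Inputs from the SAP.** Pivotal period of 24 weeks = 168 days (Section 5.1). Gap before the first extension dose of 0 to 10 days (Section 2.1). Study Day 1 = first pivotal dose, and dates before it carry no +1 (Section 4.3.3).

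**Assumptions not in the SAP.** First-dose dates are spread evenly over a 365-day year, onsets are spread evenly over the 168 pivotal days, and the event did not end before the extension start.

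**Year only known.** The rule compares the event's year with the extension-start year. Pivotal onset precedes the extension start by 1 to 168 days, 84.5 on average (94.5 with a 10-day gap).

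- Set to the extension start: 1 − 84.5/365 = 76.8%. With the 10-day gap: 1 − 94.5/365 = 74.1%.
- The remaining 23.2% (25.9%) go to January 1 of a year before the extension-start year. That always precedes Day 1, because the first dose then falls in the second half of that year.
- None keeps a date inside the pivotal period.

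The chance that the two start dates share a calendar year, 1 − 168/365.25 = 54%, is not the relevant quantity, because the rule does not look at the year of the first pivotal dose.

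**Only the day missing.** In a month of n days, summing over possible start days gives n(n−1)/2 onset days that precede the extension start within its month. Over the year this is 7×465 + 4×435 + 378 = 5,373, or 5,373/365 = 14.7 days per woman.

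- Set to the extension start: 14.7/168 = 8.8% with no gap. With a 10-day gap the sum is 7×210 + 4×190 + 153 = 2,383, giving 6.5/168 = 3.9%.
- Set before Day 1: the count for the first-dose month is the same 14.7 days, so 8.8% with either gap.
- The remaining 82.5% (87.4%) stay in the pivotal period.

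**Size of the shift before Day 1, day-missing case.** In a 30-day month, a first dose on day d gives a shift of d − 1 days and leaves 31 − d days for an onset in that month. The event-weighted mean is Σ(d−1)(31−d) / Σ(31−d) = 4,495/465 = 9.7 days.

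**Worked cases (invented dates, no gap).**

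| First pivotal dose | Extension start | True onset | Known | Imputed |
|---|---|---|---|---|
| 10 Jan 2019 | 27 Jun 2019 | 5 Mar 2019 (Day 55) | year | 27 Jun 2019 (Day 169) |
| 15 Sep 2018 | 2 Mar 2019 | 20 Oct 2018 (Day 36) | year | 1 Jan 2018 (Day −257) |
| 15 Sep 2018 | 2 Mar 2019 | 25 Sep 2018 (Day 11) | month, year | 1 Sep 2018 (Day −14) |

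The second and third cases fall in no time-to-onset band, because the first band opens at Day 1.

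**Same rules anchored on the first pivotal dose.** No pivotal-onset event lands at or after the extension start and none before Day 1. That anchor alone would pull same-year extension events back to pivotal Day 1, so the study of record has to enter the rule.

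**The case against.** The strongest reply concerns scope. Section 9.1 describes collection of adverse events from the first open-label dose, which fits an extension anchor. The pivotal events were analysed under a separate pivotal SAP, which this plan cites, and may arrive with dates already imputed. That is possible, but this SAP does not say so. Section 4.4.2 speaks of the safety analyses without restriction, and its rule for a wholly missing start date refers to the pivotal treatment start, which suggests that pivotal events are in scope.

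Three further points stand and limit the concern.

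- A reader might infer that affected events drop out as not treatment-emergent. The date-part comparison and the default for doubtful cases should keep them in. Neither repairs the onset date.
- A reader might infer that the first-onset-during-extension tables will certainly be wrong. The stated purpose of the imputed dates is to settle treatment emergence, and Section 9.1 does not define first onset during the extension. It could be taken from the study that recorded the event. Use of the imputed date is the natural reading, but it is not stated.
- A reader might infer that a placebo-period event moves into a relugolix column. Section 4.2.2 groups safety data by treatment received in the pivotal study, so the event stays in its column whatever its date.

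Also, for the same-year and same-month rules, an event that ended before the extension start is not moved, although the section then gives no fallback date. All analyses are descriptive.

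**Conclusion.** The mismatch is real as written. A pivotal event not ended before rollover is dated to the extension start when only its year is known and matches the extension-start year, or when only its day is missing and its month matches. If the first-onset tables use imputed dates, it appears there as a new onset. A day-missing event in the month of first pivotal dose, or a year-only event from a year before the extension-start year, is usually placed before Study Day 1 and fits no time-to-onset band. The January 1 rule does not reach every year-only event from the first-dose year: where that is also the extension-start year, the extension-start rule applies.

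The percentages describe only events with partial dates and rest on the uniform-date and not-yet-ended assumptions. The SAP gives no count of such events. Pooled incidence does not change. This is a minor defect in timing displays that is worth correcting because the correction is cheap.

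**What to change.** In Section 4.4.2, impute by the study that recorded the event.

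- **Recorded in the pivotal study:** where the known year (and month, if known) matches the first pivotal dose, use that dose date. Otherwise use the first of the month or January 1, not earlier than the first pivotal dose unless the known date parts or the end date show that the event began before it. The result must always precede the extension start.
- **First recorded in the extension:** keep the present extension-start rules.

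If pivotal dates are instead carried over as imputed under the pivotal SAP, say so and limit Section 4.4.2 to extension-recorded events. In either case, state in Section 9.1 which date or source defines first onset during the extension.

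The cost is revised wording of the start-date rules and a programming condition. No new data are needed, and Section 1 allows the SAP to be amended before database lock for the final report.
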